***Safety***

- Percentage of subjects with any AE leading to subject's withdrawal from the trial - from the day of vaccination

[figure not shown]
through Day 210 (Cohort 1) and Day 293 (Cohort 2).

The exploratory endpoints for this trial are:

CCI

CCI

**Statistical Considerations:**

This trial, within each age stratum in both cohorts, is to evaluate the immunogenicity and safety of four formulations (A – D), under two different dosing regimens (ie, 1 or 2 doses in Cohort 1 and 2 or 3 doses in Cohort 2). The age groups are used as a stratification factor during randomization. The trial factors under investigation include: formulation arms (4), number of doses (2 levels within each group), and age (4 age groups with Groups 2 and 2a in the same age range). For summary purpose, there are 8 formulation arms in the study within each age group, which is defined by the combination of formulation arm and number of doses.

**Analysis of Demographics and Other Baseline Characteristics**

Summaries of age, gender, race, and other baseline characteristics will be presented by formulation arm for each age group.

**Immunogenicity Analysis**

Descriptive statistics for the primary, secondary and exploratory endpoints, including estimates of seroresponse ( $\geq 4$ -fold rises), and 95% confidence intervals (CI) will be provided. Summaries will be provided by formulation arm (ie. combination of formulation arms and number of doses), and age group. Additional summaries will be provided at the cohort level, by pooling subjects across the relevant age groups, if applicable.

CCI

**Safety Analysis**

Reactogenicity will be assessed for 7 days following each vaccination via collection of solicited AEs, including local events (injection site: pain, erythema, induration, and swelling) and systemic reactions of headache, fatigue, myalgia, arthralgia, vomiting (number per day/intensity), and diarrhea (number per day/consistency) for children aged 4 to <9 years; and irritability/fussiness, drowsiness, loss of appetite, vomiting (number per day/intensity), and diarrhea (number per day/consistency) for children aged 6 weeks to <4 years daily through Day 7 after each vaccination. In addition, other indicators of reactogenicity will be collected (body temperature). Solicited reactogenicity data will be captured daily on the day of vaccination and the following 6 days.

For each solicited AE and other reactogenicity endpoints, the percentage of subjects will be summarized by event severity for each day for the 7 days after each vaccination and overall. In addition, summaries will be provided for the intervals of 1 to 3 days and 4 to 7 days after each vaccination. A summary of the first onset of each event and the number of days subjects reported experiencing each event will also be provided. For subjects with more than 1 episode of the same event, the maximum severity will be used for tabulations.

Unsolicited AEs, and SAEs, will be coded using the Medical Dictionary for Regulatory Activities (MedDRA) and summarized by system organ class (SOC) and preferred term (PT) for each formulation arm. AEs leading to subject's withdrawal from the trial will also be summarized.

**Sample Size Justification:**

This trial is designed to be descriptive and is not based on testing formal null hypotheses, and therefore the sample size was not determined based on formal statistical power calculations.

**CONFIDENTIAL**

**Interim Analysis:**

Interim analyses will be performed after the primary safety and immunogenicity data (28 days after last dose) are available (ie, Day 57 for Cohort 1 and Day 140 for Cohort 2) (primary analysis time point). Day 57 IA for Cohort 1 will be provided initially for Groups 1 and 2, who will complete Day 57 substantially earlier than Groups 2a and 3. The Day 57 IA for Groups 2a and 3 combined will be provided at a later time. Thus, the Day 57 IA will be conducted in two parts to be followed by the Day 140 IA in Group 4. All interim analyses will be performed by a separate set of unblinded statisticians and programmers at the CRO, Quintiles, who will have access to individual treatment assignments but will not otherwise be involved in study conduct. The rest of the personnel involved in the conduct of the study, including those at Takeda, Quintiles, and the study sites, will remain blinded to the individual subject data (including treatment assignments) until unblinding after database lock (Day 210 for Cohort 1 and Day 293 for Cohort 2).

More details on the analyses will be provided in the SAP.

**Data Monitoring Committee:**

An independent program level DMC will assess safety data on an ongoing basis. The DMC will also have study level responsibilities to review data and make recommendations about the sequential enrollment of various groups and formulation arms in this study.

Enrollment in this study will be initiated sequentially based on age groups and formulation arms, with ongoing DMC review.

**NOR-202 Version 4.0 (1 March 2016)**

## 2.1 Schedule of Trial Procedures

**Table 2-a Schedule of Trial Procedures for Subjects Aged 6 Months to Less Than 9 Years (Cohort 1 for Groups 1, 2 and 3; N=360)**

Procedure	Timing									
	Day 1	Day 3	Day 8	Day 29	Day 32	Day 36	Day 57	Day 134	Day 210 a	
Visits	X		X	X		X	X		X	
Phone Contacts b		X			X			X		
Visit Window (days)	-	-1/+2	+3	+3	-1/+2	+3	+3	±7	+7	
Signed Informed Consent	X									
Physical Examination c	X		(X)	X		(X)	(X)		(X)	
Trial Vaccine Administration	X d			X d						
Diary Card Dispensing	X			X						
Diary Card Delivery			X	X		X	X			
AEs e	Day 1-28			Day 28-56						
SAEs f	X	X	X	X	X	X	X	X	X	
Blood Draw for Serology (2 mL) g	X			X		X			X	
CCI	X h			X			X			

CONFIDENTIAL

Use of (X) indicates that samples or procedures that generally will not be performed but may be performed to investigate an AE, previous laboratory abnormality, or at the time of premature discontinuation.

Footnotes:

- a. **Day 210 is the 6-month end of study visit.**
- b. Phone contacts are only reminder calls on Days 3 and 32; phone contact on Day 134 is for safety data collection (Sections 9.3.5 and 9.3.6).
- c. Complete at the first visit (Day 1), brief physical exam at each vaccination, and symptom-directed thereafter. If a subject early terminates (ET), Day 210 procedures should be performed.
- d. All subjects receive NoV vaccine at Day 1; subjects in the 1 dose groups in Cohort 1 receive a saline placebo injection at Day 29 whereas subjects in the 2 dose groups in Cohort 1 receive NoV vaccine at Day 1 and Day 29.
- e. AEs will be categorized by the investigator by severity (mild, moderate, or severe) and causality (related or not related to vaccine).
- f. SAEs will be reported to the sponsor within 24 hours of the investigator becoming aware of the event.
- g. Blood draw for serology at 4 visits (all subjects); 2 mL per time point for a total of 8 mL. Anti-NoV specific GI.1 and GII.4 VLP antibodies by Pan-Ig ELISA, **CCI** and HBGA antibody assays; GMT, GMFR, and seroresponse rate ( $\geq 4$ -fold rise from baseline) will be determined for all available subjects in each formulation group. Serum NoV IgG antibody avidity will be determined pre- and post-vaccination on Days 1, 29, and 57 as available with remaining sera.
- h. **CCI**

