**Table 2-c Schedule of Trial Procedures For Subjects Aged 6 Weeks to Less Than 6 Months (Cohort 2; N=360)**

Procedure \ Timing	Day 1	Day 3	Day 8	Day 29	Day 56	Day 59	Day 63	Day 84	Day 112	Day 115	Day 119	Day 140	Day 200	Day 260	Day 293 a
Visits	X		X	X	X		X	X	X		X	X			X
Phone Contacts b		X				X				X			X	X	
Visit Window (days)	-	-1/+2	+3	+3	+3	-1/+2	+3	+3	+3	-1/+2	+3	+7	+7	+7	+7
Signed Informed Consent	X														
Physical Examination c	X		(X)	(X)	X		(X)	(X)	X		(X)	(X)			(X)
Trial Vaccine Administration	X d				X d				X d						
Diary Card Dispensing	X				X				X						
Diary Card Delivery			X	X			X	X			X	X			
AEs e	Day 1-28				Day 56-84				Day 112-140						
SAEs f	X	X	X	X	X	X	X	X	X	X	X	X	X	X	X
Blood Draw for Serology (2 mL) g	X				X			X			X				X

CONFIDENTIAL

Use of (X) indicates that samples or procedures that generally will not be performed but may be performed to investigate an AE, previous laboratory abnormality, or at the time of premature discontinuation.

Footnotes:

- a. Day 293 is the 6-month end of study visit.
- b. Phone contacts are only reminder calls on Days 3, 59, and 115; phone contact on Days 200 and 260 are for safety data collection (Sections 9.3.5 and 9.3.6).
- c. Complete at the first visit (Day 1), brief physical examination at each vaccination, and symptom-directed thereafter. If a subject early terminates (ET), Day 293 procedures should be performed.
- d. Investigational study doses will be given at least 28 days before and/or after routine pediatric vaccines given per the national vaccine program. NoV bivalent VLP study doses for the 3 dose groups are given at Days 1, 56, and 112. NoV bivalent VLP vaccine for the 2 dose groups are given at Days 1 and 56 with a saline placebo injection given on Day 112.
- e. AEs will be categorized by the investigator by severity (mild, moderate, or severe) and causality (related or not related to vaccine).
- f. SAEs will be reported to the sponsor within 24 hours of the investigator becoming aware of the event.

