### **9.1.6      Immunogenicity Assessments**

Subjects in Cohort 1 in all vaccine arms will undergo blood sampling for serological immunogenicity testing on Day 1 (prior to the first vaccination), Day 29 (prior to the second vaccination), Day 57 (28 days after the second vaccination), and Day 210; Subjects in Cohort 2 will undergo blood sampling for serological testing on Day 1 (prior to the first vaccination), Day 56 (prior to the second vaccination), Day 84 (28 days after the second and 28 days prior to the third vaccination), Day 140 (28 days after the third vaccination), and Day 293. To alleviate the pain associated with blood sampling in this pediatric population, blood collection will be performed by experienced, trained personnel who routinely obtain blood from infants and children, under the supervision of the Principal Investigator after optional application of EMLA cream/patch and using pediatric size needles. All blood samples will be collected in accordance with acceptable laboratory procedures. For serology in all subjects, the volume of blood taken at any single visit is approximately 2 mL. For subjects (without CMI testing), the approximate total volume of blood in the trial is 8 mL for Cohort 1 subjects in Groups 1, 2, 2a, and 3 (4 blood draws) and 10 mL for Cohort 2 subjects in Group 4 (5 blood draws). For those subjects with CMI, a subset of the subjects aged  $\geq$  3 years at selected sites in Groups 1 and 2 only, an additional volume of 3 mL of blood at each of three time points will be drawn immediately prior to and approximately 28 days after each vaccination (Days 1, 29, and 57) for a subtotal of approximately 9 mL. To clarify, for those children aged 3 years and older selected to be in the CMI subset in Groups 1 and 2 only, a total of 17 mL per subject will be obtained for the entire study period. Because subjects in Group 2a will not participate in CMI testing, the total volume of blood for Group 2a subjects is 8 mL. Likewise, the total volume of blood for Group 3 subjects remains at 8 mL. To clarify, for the youngest infants, those in Cohort 2 (Group 4), a total of 10 mL per subject will be obtained for the entire study period. All blood samples will be processed and stored at the trial site according to the Laboratory Guidelines as provided in the Procedures Manual.

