#### Baseline Definition and Windowing Conventions

Study Day 1 is defined as the date of the first vaccination, as recorded on the eCRF vaccination page. Other study days are defined relative to Study Day 1, with Day -1 being the day prior to Day 1. In addition, day relative to vaccination will be derived for each vaccination dose. For example, day relative to the first dose will be equal to the Study Day. Day relative to the second dose will start with a value of 1 on the day of the second dose and so on for each vaccination given. Day relative to dose is of use for tables presenting summaries of events relative to dose.

For listings presenting observations or events by day, both the Study Day and Day Relative to Dose will be presented.

Baseline is defined as the last non-missing measurement taken before the first dose of vaccination (Day 1), unless otherwise defined for a particular endpoint parameter.

A windowing convention will be used to determine the analysis value for a given study visit for observed data analyses. The window definitions as outlined below in [Table 7.a](#) and [Table 7.b](#) will be used for the immunogenicity (serology and CMI) and vital signs, respectively. The window conventions are:

1. A window of +/- 7 days from the target day is applied to the following visits: Study Days 29 and 57 for cohort 1 and Study Days 56, 84, 112, and 140 for cohort 2;
2. A window of +/- 28 days from the target day is applied to the following visits: Study Day 210 for cohort 1 and Study Day 293 for cohort 2.

The windows for immunogenicity are constructed by dosing period relative to actual dosing day. Windows for vital signs are constructed relative to the actual study day.

One or more results for a particular immunogenicity or vital sign variable may be obtained in the same visit window (see study window definitions in [Table 7.a](#) and [Table 7.b](#)). In such an event, the result with the date closest to the expected visit date will be used. In the event that 2 observations are equidistant from the expected visit date, the later observation will be used.

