## **7.8 Immunogenicity Analysis**

### *General Methodology*

The primary population for immunogenicity analyses will be the PPS. Supportive immunogenicity analyses on primary and key secondary endpoints will also be performed using FAS.

Descriptive statistics for the primary, secondary, and exploratory endpoints will be computed for all available assays at all relevant time points and include the following:

- Titer values (eg, GMT, BT50, GMFR): geometric mean, GSD, 95% CIs, minimum, and maximum;
- Other continuous endpoints: mean, SD, median, minimum, and maximum;
- Categorical variable (eg, seroresponse rate): number and percentage of subjects, and 95% CIs in specified categories. The 95% CI of seroresponse rate will be calculated using exact (Clopper-Pearson) method.

Cohorts will be analyzed separately due to different number of doses (1 or 2 in Cohort 1; 2 or 3 in Cohort 2).

Analysis of covariance (ANCOVA) will be conducted for continuous outcome parameters (eg, GMT, GMFR), examining the effect of formulation/dose combination using log-transformed values of the endpoint as the dependent variable and the corresponding log-transformed baseline (pre-vaccination) value as a continuous covariate. The ANCOVA models will include group as a factor for analyses of Cohort 1 with a group by formulation/dose combination interaction term if

appropriate as follows. If the interaction term p-value is  $\leq 0.05$ , the term will remain in the model. If the p-value is  $>0.05$  it will be removed. For Cohort 1, the model will include estimates for treatment (formulation/dose combination) effect within each group, and at the cohort level across groups. A factor for country will be included in all models.

For binomial outcomes the Cochran-Mantel-Haenszel (CMH) method [2] for difference in proportions will be conducted, stratified by group (Cohort 1).

All pairwise comparisons (with the lower level as a reference group) will be presented, without adjustments for multiplicity.

Pre-specified comparisons of interest will be tested. The pre-specified comparisons of interest are the following:

- “A: 15/15, 1 Dose” vs. “A: 15/15, 2 Dose”
- “A: 15/15, 1 Dose” vs. “B: 15/50, 2 Dose”
- “B: 15/50, 1 Dose” vs. “C: 50/50, 1 Dose”
- “B: 15/50, 1 Dose” vs. “B: 15/50, 2 Dose”
- “C: 50/50, 1 Dose” vs. “B: 15/50, 2 Dose”
- “C: 50/50, 1 Dose” vs. “C: 50/50, 2 Dose”
- “C: 50/50, 1 Dose” vs. “D: 50/150, 2 Dose”
- “D: 50/150, 1 Dose” vs. “D: 50/150, 2 Dose”

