#### Secondary and Exploratory Continuous Immunogenicity Endpoints

The secondary and exploratory continuous immunogenicity endpoints are listed below:

- CCI
- 
- 
- 
- 
- 
- 
- 

GMT, BT50 and GMFR will be summarized descriptively, as described in the General Methodology of Section 7.9, for each of the 8 formulation/dose combinations (4 formulation arms; 1 and 2 [or 2 and 3] doses), by group, at each scheduled time point. These summaries will

also be provided at the cohort level, ie, by pooling subjects across the relevant groups. These summaries will be provided for the subjects in the PPS and FAS.

The GMT and BT50 will be calculated as the anti-logarithm of  $\sum(\log \text{transformed titer}/n)$ , ie, as the anti-logarithm transformation of the mean of the log-transformed titer, where n is the number of subjects with titer information. The GSD for GMT and BT50 will be calculated as the anti-logarithm transformation of the standard deviation of the log-transformed titer. The 95% CI will be calculated as the anti-logarithm transformation of the upper and lower limits for a two-sided CI for the mean of the log-transformed titers.

[figure not shown]
GMFR will be calculated as anti-logarithm of  $\sum (\log \text{transformed (post-vaccination titer/ pre-vaccination titer)}/n)$ . The GSD and 95% CIs for GMFR will be calculated similarly to those for GMT and BT50.

GMT, BT50 and GMFR will be analyzed with an ANCOVA model examining the effect of formulation/dose combination using the log-transformed value as the dependent variable and the corresponding log-transformed baseline value as a covariate. The ANCOVA models will include group as a factor for analyses of Cohort 1 with a group by formulation/dose combination interaction term included if appropriate, as follows. If the interaction term p-value is  $\leq 0.05$ , the term will remain in the model. If the p-value is  $>0.05$  it will be removed. For Cohort 1, the model will include estimates for treatment (formulation/dose combination) effect within each group, and at the cohort level across groups. A factor for country will be included. All the applicable pairwise comparisons will be provided with lower levels as the reference groups, with no adjustments for multiplicity. The 14 comparisons of interest listed in the *General Methodology* of Section 7.8 will be tested. The analyses will be based on the PPS.

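### For the within-formulation dose-number contrasts, the titre drawn before the last injection is a valid covariate that the SAP leaves unused; the planned intervals are valid but may be wider than they need be

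*Protocol*

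**What the plan says.** **Treatment up to the last injection.** Protocol 2.1, Table 2-a footnote d, states "All subjects receive NoV vaccine at Day 1" and then "subjects in the 1 dose groups in Cohort 1 receive a saline placebo injection at Day 29", while the 2-dose arms receive vaccine again. Table 2-b says the same for Group 2a. For Cohort 2, Table 2-c footnote d states "NoV bivalent VLP vaccine for the 2 dose groups are given at Days 1 and 56 with a saline placebo injection given on Day 112"; the 3-dose arms differ only at Day 112.

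**Blood draws.** Protocol 9.1.6 places the Cohort 1 sample at "Day 29 (prior to the second vaccination"). In Cohort 2 the last sample before the final injection is "Day 84 (28 days after the second and 28 days prior to the third vaccination"). No draw is listed for Day 112.

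**Model.** SAP 7.1 fixes the reference value: "Baseline is defined as the last non-missing measurement taken before the first dose of vaccination (Day 1"). The ANCOVA in SAP 7.8 uses the "corresponding log-transformed baseline (pre-vaccination) value as a continuous covariate", with group (Cohort 1) and country as factors. SAP 7.8.2 repeats this for GMT, BT50 and GMFR, "using the log-transformed value as the dependent variable and the corresponding log-transformed baseline value as a covariate". The primary seroresponse analysis (SAP 7.8.1) is CMH stratified by group and has no titre covariate.

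**Contrasts.** SAP 7.8 lists 14 comparisons. Four are within-formulation dose-number contrasts: A1–A2, B1–B2, C1–C2 and D1–D2. The 2 versus 3 dose contrasts of Cohort 2 come under the general provision for all pairwise comparisons.

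**The concern.** Within a formulation, the two dose-number arms have had identical injections when the Day 29 sample (Cohort 1) or the Day 84 sample (Cohort 2) is taken. Assignment is randomised, so it cannot have changed that titre. For this one type of contrast the titre is therefore a pre-treatment covariate in the ordinary sense, although it comes after the first dose.

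This titre carries each child's response to the earlier dose or doses, which may predict the endpoint titre beyond what Day 1 predicts. Where it does, the planned model leaves that variation in the residual.

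The contrast matters because Protocol 4.2 and 6.2 make the number of doses one of the things the trial should inform. The trial is descriptive and has no power calculation, so what it can say about schedule depends largely on interval width. Arms are small: about 15 per group in Cohort 1, and about 45 in Cohort 2.

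**Working it through.** **1. The plan's own figure.** The only sample-size calculation is Protocol Table 13-a. It reproduces: 1 − (1 − 0.0033)^480 = 79.5%. It concerns detecting an adverse event and says nothing about precision for a dose-number contrast.

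**2. Inputs.** Arm sizes come from Protocol 6.1: 120/8 = 15 per arm per group, 4 × 15 = 60 per arm over four groups, and 360/8 = 45 in Cohort 2. The documents give no titre SD, effect size or correlation. Let r be the partial correlation of the pre-last-injection log titre with the endpoint log titre, given Day 1. It is an assumption, shown over a range.

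**3. Continuous endpoints.** Adding the titre multiplies the residual SD, and so the interval width, by √(1−r²). The equivalent sample-size factor is 1/(1−r²). The last column is a simulation of the ANCOVA (8 arms × 4 groups × 15, Day 1 covariate and group; country omitted), with and without the Day 29 titre.

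| Assumed r | √(1−r²) | 1/(1−r²) | Simulated width ratio |
|---|---|---|---|
| 0 | 1.00 | 1.00 | 1.001 |
| 0.3 | √0.91 = 0.95 | 1.10 | 0.955 |
| 0.5 | √0.75 = 0.87 | 1.33 | 0.867 |
| 0.7 | √0.51 = 0.71 | 1.96 | 0.714 |
| 0.8 | √0.36 = 0.60 | 2.78 | not run |

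For r from 0 to 0.7, with a true dose-number effect of 0.30 log10, the Day 29-adjusted estimates were 0.296 to 0.302. Coverage was 94.8% to 95.5%, against 94.0% to 96.0% under the SAP model. Both are valid. With unequal correlations in the two arms (0.9 after saline, 0.5 after a second dose) the ratio was 0.72. In a model of two arms only, a rough allowance for estimating one more slope raises these factors by no more than about 1% at 45 or 60 per arm, and about 4% at 15.

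**4. Where the covariate must not go.** Between formulations, the Day 29 titre is itself an outcome of treatment. Entered as a plain covariate in the single 8-arm model, it took a true D2–A2 difference of 0.30 down to 0.15 at r = 0.5 and 0.09 at r = 0.7. The SAP model gave 0.30 and 0.29. Centring the titre within formulation and group kept nearly all the gain for the dose-number contrast (width ratio 0.87 at r = 0.5, 0.73 at r = 0.7).

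**5. Seroresponse.** Assume true rates of 60% and 80%, 60 per arm, four equal groups and a single latent response. The stratified risk difference was compared with a logistic-standardised risk difference that uses the earlier response.

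| Latent r | SE, stratified | SE, adjusted | Ratio | 95% half-width, points |
|---|---|---|---|---|
| 0 | 0.0820 | 0.0822 | 1.00 | 16.1 → 16.1 |
| 0.3 | 0.0817 | 0.0793 | 0.97 | 16.0 → 15.6 |
| 0.5 | 0.0825 | 0.0771 | 0.94 | 16.2 → 15.1 |
| 0.7 | 0.0809 | 0.0688 | 0.85 | 15.9 → 13.5 |

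Both estimators averaged about 0.20, the true difference. The real endpoint requires a rise to both antigens, so this is indicative only.

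**The case against.** **It is an efficiency preference.** The planned ANCOVA and CMH intervals have correct coverage. The trial is stated to be descriptive, and only four of the 14 listed comparisons are involved. This stands, and it fixes the weight of the point. A reader might go on to call the dose-number comparison underpowered, but the documents set no power target or effect size against which to say so.

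**The gain is unknown.** This also stands. A reader might infer that the intervals are certainly too wide. The documents give no correlation, so the range runs from no gain to a large one. The loss at r near zero is small.

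**Day 84 is not immediately before the last injection.** Correct: it is 28 days before the third injection and 56 days before Day 140. The arms are still identically treated at that time, so the covariate is valid, but its correlation with the endpoint may differ from that in Cohort 1.

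**Practical difficulties.** Three are real:
- The SAP window for Day 29 (Days 22–36 after dose 1) does not itself require a sample taken before dose 2.
- The per-protocol set does not require a Day 29 or Day 84 sample, and SAP 7.1 rules out imputation apart from dates and values below the LLoQ (multiple imputation may be explored only if more than 20% lack the primary endpoint).
- A1–A2, A2–B2 and A1–B2 are all listed and add up under one model. They need not add up if A1–A2 comes from another.

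The first two can be met by drafting; the third is a cost to accept.

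**Redaction.** SAP 7.8.3 and the exploratory lists are blacked out, so an additional analysis there cannot be excluded. The general model that governs these contrasts is visible.

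**Conclusion.** The point holds as a cheap improvement in precision. For within-formulation dose-number contrasts, the Day 29 titre drawn before the second injection (Cohort 1) or the Day 84 titre (Cohort 2) is a legitimate covariate, is already scheduled, and does not appear in the visible models.

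The size rests entirely on the assumed r. For the ANCOVA endpoints, width would fall by about 5% at r = 0.3, 13% at 0.5, 29% at 0.7 and 40% at 0.8, and not at all at r = 0. For seroresponse the SE would fall by about 3%, 6% and 15% at latent r = 0.3, 0.5 and 0.7. The 60 per arm assumes pooling over all four Cohort 1 groups.

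Three stronger readings are not supported. The planned results are not biased. It is not true that every contrast is adjusted for Day 1, since the primary CMH analysis uses no titre. Nor may the later titre be added to the whole model, because that would bias the contrasts between formulations.

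**What to change.** In SAP 7.8 and 7.8.2, for the within-formulation dose-number contrasts only:

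- **Continuous endpoints.** Add an ANCOVA fitted separately within each formulation, or with the later titre centred within formulation and group. Covariates are log Day 1 titre plus log Day 29 titre (Cohort 1) or log Day 84 titre (Cohort 2), with group (Cohort 1) and country.
- **Seroresponse.** Add a covariate-adjusted risk difference using the same titres, as a supportive analysis beside the CMH result. The reference that the SAP already cites for its CMH method is on covariate-adjusted differences in proportions.
- **Sample rule.** Use only Day 29 samples drawn before the second injection, whatever the visit window allows.
- **Missing Day 29 or Day 84 titres.** Use a likelihood-based repeated-measures model whose Day 29 (or Day 84) means are constrained equal across the two dose arms of a formulation. It needs no imputation, so it is consistent with SAP 7.1.
- **All contrasts between formulations.** Keep the Day 1-only model.

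The cost is a paragraph in the SAP and a second model per endpoint, with no new visit, sample or assay. The report should say that dose-number estimates and between-formulation estimates come from different models and need not add up exactly.
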